5.3.1 Definition of Dose-Limiting Toxicity (DLT)

Dose-limiting toxicities are defined as any hematologic or non-hematologic toxicity of grade 3 or above possibly attributable to drug that does not resolve within 12 weeks with or without steroids (and steroids

must be able to be tapered to <10 mg po qd within that time frame). Although the DLT period is officially the 1st two cycles, if any participant experiences a grade 3, 4, or 5 toxicity, they will be closely monitored. If those participants are not able to resume treatment within 6 weeks (2 cycles), enrollment into cohorts A and B will be halted to allow for a full 12 week evaluation prior to further enrollment.

For cohorts A and B only: initially 3 participants will be enrolled. When those three participants have completed the DLT evaluation period (2 cycles), if 0 of 3 have experienced a DLT (defined as hematologic or non-hematologic toxicity of grade 3 or above possibly attributable to drug that does not resolve within 12 weeks with or without steroids), the study may continue to enroll an additional 3 participants for DLT monitoring. If 1 of 3 participants experiences a DLT, an additional 3 participants will be enrolled and followed. If ≥ 2 participants experiences a DLT (either when 3 or when 6 enrolled), further enrollment will be halted for discussion between Merck and the overall PI to determine whether additional enrollment should continue or if dose modifications should be made. If no more than 1 of 6 participants experiences a DLT, full enrollment of the cohort may proceed.

Management and dose modifications associated with the above adverse events are outlined below.

Number of Participants with DLT during initial 3 participant enrollment	Continuation Decision Rule
0 out of 3	Enroll 3 additional participants and monitor for DLT.
≥ 2	Further enrollment will be stopped until discussions re: dose modification between Merck and overall PI determine whether further dose levels should be explored.
1 out of 3	Enter at least 3 more participants and monitor for DLT. 
• If 0 of these 3 participants experience DLT, proceed with complete enrollment of the cohort.• If 1 or more of this group suffer DLT, then further enrollment will be stopped until discussions re: dose modification between Merck and overall PI determine whether further enrollment should continue and if dose modification is required.

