4. TRIAL PROCEDURES

Prior to treatment, a screening period of 28 days will consist of baseline CT and MRI scans as indicated, complete blood count, complete metabolic profile, TSH, blood for research studies as outlined below, and pulmonary function tests.

Day 1 of each cycle will include MD/NP visit, labwork as above, and treatment.

For cohorts A and B, in which pembrolizumab is given in combination with platinum and etoposide, initial enrollment will include only 3 participants. Once these three participants have been enrolled to either cohort A or B, enrollment will be halted until these participants have cleared cycle 1. An additional 3 participants (into either cohort A or B) may be enrolled if no DLTs are seen. If < 2 DLTs are seen in the first 6 participants, enrollment to the rest of the cohort will proceed. If ≥ 2 DLTs are seen, enrollment will be halted and discussion of dosing change amongst the investigators will occur prior to further enrollment. Based on safety data to date with other platinum-based regimens, we do not anticipate interactions that would necessitate dosing change.

Because there is limited data on the combination of pembrolizumab with radiotherapy, for cohorts A and B, pembrolizumab dosing will be held 2 weeks prior to the start of radiation (i.e. radiotherapy could start at completion of last cycle of pembrolizumab) and resumed 2 weeks after completion of radiation (resulting in 2 missed doses of pembrolizumab)

[figure not shown]

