FOR COHORTS A AND B ONLY: Initial enrollment will include only 3 participants, who may be enrolled into either cohort A or B. Once these three participants have cleared cycle 1, an additional 3 participants may be enrolled into either cohort A or B if no DLTs are seen. If < 2 DLTs are seen in the first 6 participants, enrollment to the rest of the cohorts will proceed. If ≥ 2 DLTs are seen, enrollment will be halted and discussion of dosing change with Merck and the overall PI will occur prior to further enrollment. Based on safety data to date with other platinum-based regimens, we do not anticipate interactions that would necessitate dosing change, so there will not be pre-specified dose reductions planned. Cohorts A and B will be pooled for the purposes of DLT evaluation as the treatment regimen after study initiation is identical.

Cohort C: participants will have previously received 4-6 cycles of platinum-based therapy and have stable disease. In addition, these patients must not be candidates for further consolidation thoracic radiotherapy or PCI. Pembrolizumab treatment should start no sooner than 2 weeks and no later than 6 weeks from the start of the last cycle of chemotherapy. Therapy will continue for up to 34 cycles (2 years).

Cohort D: participants will have previously received 4-6 cycles of platinum-based chemotherapy and thoracic radiation therapy or PCI or both. Pembrolizumab treatment should start no sooner than 2 weeks and no later than 6 weeks from the start of the last dose of radiation. Therapy will continue for up to 34 cycles (2 years).

Treatment will be administered on an outpatient basis. Reported adverse events and potential risks are described in Section 1.8.1. Appropriate dose modifications are described in Section 5. No investigational or commercial agents or therapies other than those described below may be administered with the intent to treat the participant's malignancy.

All patients will be required to have a tissue biopsy within 3 weeks of study entry and after completion of prior therapy (see section 6.6.7.1). For cohort A, this time frame could be up to 6 weeks.

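### The cohort A/B safety run-in states two different rules for its first decision, and some toxicities can still be unclassifiable when a decision is taken

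*Combined protocol and SAP*

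**What the plan says.** The run-in pools cohorts A and B: three participants, then three more, then the rest. Synopsis section 4 (Trial Procedures) says that "enrollment will be halted until these participants have cleared cycle 1", and then: "An additional 3 participants (into either cohort A or B) may be enrolled if no DLTs are seen". Section 5.3 repeats the timing, "Once these three participants have cleared cycle 1, an additional 3 participants may be enrolled", again only with zero DLTs. Neither text gives an action at 1 of 3. On the second decision section 5.3 says: "If < 2 DLTs are seen in the first 6 participants, enrollment to the rest of the cohorts will proceed". The synopsis agrees.

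Section 5.3.1, to which section 1.6.1 sends the reader for details, places the first decision later: "When those three participants have completed the DLT evaluation period (2 cycles" and none has had a DLT, three more may enter. It adds: "If 1 of 3 participants experiences a DLT, an additional 3 participants will be enrolled and followed". Its decision table says the same. It defines a DLT as "any hematologic or non-hematologic toxicity of grade 3 or above possibly attributable to drug that does not resolve within 12 weeks".

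Section 5.3.1 also recognises that its window and its definition differ in length. After "Although the DLT period is officially the 1st two cycles" it requires close monitoring of any grade 3–5 toxicity. If the participant cannot resume treatment within 6 weeks, A/B enrolment stops for a full 12-week evaluation. It does not say when the 6-week and 12-week clocks start. Table 3 in section 5.3.2 counts its 12 weeks from the last dose.

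**The concern.** This is the only prespecified numerical safety rule for enrolment to pembrolizumab plus platinum–etoposide. There are two problems.

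First, the texts differ on when the first decision is taken and on what permits it. Under the synopsis or section 5.3, the decision comes halfway through the DLT window that 5.3.1 sets (21 of 42 days). At 1 of 3, section 5.3.1 enrols three more, while the other two texts give no permission and no alternative.

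Second, a DLT is defined by non-resolution at 12 weeks, but the decision is read at week 3 or week 6. A qualifying toxicity may be pending while the count is recorded as 0 of 3, or as 0 or 1 of 6. The first decision admits three participants. The second opens the remaining A/B places, 2 × 15 − 6 = 24.

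**Working it through.** The plan states no operating characteristic for the run-in, so there is no figure to reproduce. The check compares the texts and then does the calendar arithmetic.

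**Inputs.** Cycle length 21 days (section 5.3). DLT window two cycles, 12-week criterion and 6-week halt (section 5.3.1). Dose holds and restarts (section 5.3.2 and Table 3). Cohort size 15 (synopsis section 3).

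**1. The rules side by side**

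| | Synopsis 4 and section 5.3 | Section 5.3.1 |
|---|---|---|
| First decision read | after cycle 1, day 21 | after two cycles, day 42 |
| 0 of 3 | three more | three more |
| 1 of 3 | no action stated | three more |
| 2 or more | halt and discuss | halt and discuss |
| Full enrolment | fewer than 2 of 6 | at most 1 of 6 |
| Second decision read | not stated | not stated, implied by the two-cycle window |

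The last two rows agree in substance. The conflict is in the timing of the first decision and at 1 of 3.

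**2. How likely is 1 of 3?** The probability is 3p(1 − p)². The DLT rates p are assumptions, since the plan gives none. The last two rows show the chance of clearing to full enrolment if silence at 1 of 3 is read as a stop, and under 5.3.1.

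| True DLT rate | 10% | 20% | 30% | 40% |
|---|---|---|---|---|
| Exactly 1 of 3 | 0.243 | 0.384 | 0.441 | 0.432 |
| Clears, silence read as stop | 0.709 | 0.459 | 0.269 | 0.140 |
| Clears, 5.3.1 | 0.886 | 0.655 | 0.420 | 0.233 |

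For example, at 20%: 3 × 0.2 × 0.8² = 0.384; 0.8³ × 0.896 = 0.459; 0.8⁶ + 6 × 0.2 × 0.8⁵ = 0.655.

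**3. When is a DLT decidable?** Days run from the last-enrolled participant's first dose, with clocks from onset. The halt falls at onset + 42 and classification at onset + 84.

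- Decision on day 21, onset day 0–21: classification on day 84–105, which is 63–84 days after the decision.
- Decision on day 42, onset in cycle 2 (day 21–42): halt on day 63–84, which is 21–42 days after. Classification is on day 105–126, which is 63–84 days after.
- Decision on day 42, onset in cycle 1 with dosing continued: classification on day 84–105, which is 42–63 days after. The halt need not trigger.

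If the clock ran from the last dose instead, with doses on days 0 and 21 and none later, the halt would fall on day 63 and classification on day 105. These are 21 and 63 days after day 42.

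**4. Which events does 5.3.1 already catch?**

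- Permanent discontinuations: Table 3 stops pembrolizumab for grade 3–4 pneumonitis, nephritis and infusion reactions, for grade 3–4 hepatic events with one exception, and for most other grade 4 toxicity. Inability to resume is known at once.
- Held cycle-1 toxicity: a participant whose dose is held does not receive cycle 2 on day 21, and section 5.3.2 restarts the cycle after a delay. Two cycles are normally not complete on day 42, so the decision is not yet due.
- Cycle-2 onset with a dose hold: caught, but only 21–42 days after the decision.
- Dosing continued or resumed before resolution: need not be caught. Table 3 lets dosing continue through grade 3–4 hypothyroidism and resume in type 1 diabetes once the patient is stable.

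**The case against.** The strongest reply is that the plan is safer than the conflicting sentences suggest. Section 1.6.1 identifies 5.3.1 as the detailed rule. The synopsis and section 5.3 are silent on 1 of 3 rather than opposed to it, and 5.3.1 supplies the branch. The limit of 1 in 6 never changes. The authors saw the mismatch between window and definition and added a halt. Other checks remain: serious adverse event reporting (10.3), conference calls after three patients and data monitoring committee review (10.5.1), and monthly adverse event review (12.1).

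Most of this stands, and it limits the consequence. It does not settle the timing. Cycle 1 and two cycles cannot both be right, section 5.3 is an operative section, and nothing says that 5.3.1 prevails. None of the other checks says how a pending toxicity counts when a decision is read.

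A reader might infer that different sites could run different rules. The documents do not support that. Sections 4.5.1 and 4.5.2 route every enrolment through central registration at the coordinating centre, so one office applies the rule. The remaining risk is that this office follows the earlier-opening text.

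A stricter rule could also hold enrolment for up to 12 weeks over a hormone-replaced thyroid disorder for which Table 3 does not withhold a dose. That objection is fair, and the fix needs an exception for it.

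**Conclusion.** The point holds on both counts. The first decision has two written rules, and one of them opens enrolment 21 days before the DLT window ends. Separately, an unresolved non-fatal grade 3+ event cannot be classified at either time. After credit for the 6-week halt, the gap at the two-cycle decision is confined to cycle-2 onsets and to toxicities through which dosing continues or resumes. For cycle-2 onsets the size is 21–42 days to the halt and 63–84 days to classification after day 42. These figures assume clocks from onset and no dose delay before the event.

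Two stronger inferences are not supported. One is that every unresolved grade 3+ event escapes the rule: permanent discontinuations and held cycle-1 events are largely covered, as shown above. The other is that 24 participants would be exposed during the gap. That number is a ceiling on the places opened. The documents give no accrual rate, and the 6-week halt still applies after the second decision.

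The run-in does not affect the primary PD-L1 endpoint. It is still worth correcting, because it is a safety rule and the correction is wording only.

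**What to change.** 1. Change synopsis section 4 and section 5.3 to the two-cycle window and the 5.3.1 rule for 1 of 3.
2. State in 5.3.1 that the six-participant decision is read after participant 6 completes two cycles.
3. State that a possibly attributable grade 3+ toxicity still unresolved at a decision does not count as no DLT. The decision waits until the toxicity resolves or reaches 12 weeks from onset. Except from this wait chemotherapy-attributed uncomplicated cytopenias, and endocrine toxicities controlled on replacement therapy for which Table 3 allows dosing. The list in section 10.4.1 is a starting point for the cytopenias, although it was written for expedited reporting.
4. Run the 12-week and 6-week clocks from onset. A last-dose clock has no bound when dosing continues.

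Cost: no extra participants. The enrolment hold is at most 126 − 42 = 84 days beyond day 42 per decision. If the maximum occurred at both decisions it would total 168 days, or 24 weeks, in a study planned for 3 years (section 5.11). For dose-held toxicities that would trigger the existing halt at onset + 42, the added hold is at most 84 − 42 = 42 days per decision.

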Hyperthyroidism	3	Toxicity resolves to Grade 0-1	Toxicity does not resolve within 12 weeks of last dose or inability to reduce corticosteroid to 10 mg or less of prednisone or equivalent per day within 12 weeks.
	4	Permanently discontinue	Permanently discontinue
Hypothyroidism	2-4	Therapy with pembrolizumab can be continued while treatment for the thyroid disorder is instituted	Therapy with pembrolizumab can be continued while treatment for the thyroid disorder is instituted.
Infusion Reaction	3-4	Permanently discontinue	Permanently discontinue
Pneumonitis	2	Toxicity resolves to Grade 0-1	Toxicity does not resolve within 12 weeks of last dose or inability to reduce corticosteroid to 10 mg or less of prednisone or equivalent per day within 12 weeks.
	3-4	Permanently discontinue	Permanently discontinue
Renal Failure or Nephritis	2	Toxicity resolves to Grade 0-1	Toxicity does not resolve within 12 weeks of last dose or inability to reduce corticosteroid to 10 mg or less of prednisone or equivalent per day within 12 weeks.
	3-4	Permanently discontinue	Permanently discontinue
All Other Drug-Related Toxicity ²	3 or Severe	Toxicity resolves to Grade 0-1	Toxicity does not resolve within 12 weeks of last dose or inability to reduce corticosteroid to 10 mg or less of prednisone or equivalent per day within 12 weeks.
	4	Permanently discontinue	Permanently discontinue

Note: Permanently discontinue for any severe or Grade 3 drug-related AE that recurs or any life-threatening event. ¹ For patients with liver metastasis who begin treatment with Grade 2 AST or ALT, if AST or ALT increases by greater than or equal to 50% relative to baseline and lasts for at least 1 week then patients should be discontinued. ² Patients with intolerable or persistent Grade 2 drug-related AE may hold study medication at physician discretion. Permanently discontinue study drug for persistent Grade 2 adverse reactions for which treatment with study drug has been held, that do not recover to Grade 0-1 within 12 weeks of the last dose.
			

Dosing interruptions are permitted in the case of medical / surgical events or logistical reasons not related to study therapy (e.g., elective surgery, unrelated medical events, patient vacation, and/or holidays). Subjects should be placed back on study therapy within 4 weeks of the scheduled

interruption, unless otherwise discussed with the Sponsor. The reason for interruption should be documented in the patient's study record.

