
Grades 3 or 4 Grade 3: Prolonged (i.e., not rapidly responsive to symptomatic medication and/or brief interruption of infusion); recurrence of symptoms following initial improvement; hospitalization indicated for other clinical sequelae (e.g., renal impairment, pulmonary infiltrates) Grade 4: Life-threatening; pressor or ventilatory support indicated
	
Stop Infusion. Additional appropriate medical therapy may include but is not limited to: IV fluids Antihistamines NSAIDS Acetaminophen Narcotics Oxygen Pressors Corticosteroids Epinephrine
 
Increase monitoring of vital signs as medically indicated until the subject is deemed medically stable in the opinion of the investigator. Hospitalization may be indicated. Subject is permanently discontinued from further trial treatment administration.
	
No subsequent dosing

Appropriate resuscitation equipment should be available in the room and a physician readily available during the period of drug administration.
		

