- **Type 1 diabetes mellitus (if new onset, including diabetic ketoacidosis [DKA]) or ≥ Grade 3 Hyperglycemia, if associated with ketosis (ketonuria) or metabolic acidosis (DKA)**
 - For **T1DM or Grade 3-4 Hyperglycemia**
 - Insulin replacement therapy is recommended for Type I diabetes mellitus and for Grade 3-4 hyperglycemia associated with metabolic acidosis or ketonuria.
 - Evaluate patients with serum glucose and a metabolic panel, urine ketones, glycosylated hemoglobin, and C-peptide.

- **Hypophysitis:**
 - For **Grade 2** events, treat with corticosteroids. When symptoms improve to Grade 1 or less, steroid taper should be started and continued over no less than 4 weeks. Replacement of appropriate hormones may be required as the steroid dose is tapered.
 - For **Grade 3-4** events, treat with an initial dose of IV corticosteroids followed by oral corticosteroids. When symptoms improve to Grade 1 or less, steroid taper should be started and continued over no less than 4 weeks. Replacement of appropriate hormones may be required as the steroid dose is tapered.

- **Hyperthyroidism or Hypothyroidism:**

Thyroid disorders can occur at any time during treatment. Monitor patients for changes in thyroid function (at the start of treatment, periodically during treatment, and as indicated based on clinical evaluation) and for clinical signs and symptoms of thyroid disorders.

 - **Grade 2** hyperthyroidism events (and **Grade 3-4** hypothyroidism):
 - In hyperthyroidism, non-selective beta-blockers (e.g. propranolol) are suggested as initial therapy.
 - In hypothyroidism, thyroid hormone replacement therapy, with levothyroxine or liothyronine, is indicated per standard of care.
 - **Grade 3-4** hyperthyroidism
 - Treat with an initial dose of IV corticosteroid followed by oral corticosteroids. When symptoms improve to Grade 1 or less, steroid taper should be started and continued over no less than 4 weeks. Replacement of appropriate hormones may be required as the steroid dose is tapered.

- **Hepatic:**
 - For **Grade 2** events, monitor liver function tests more frequently until returned to baseline values (consider weekly).
 - Treat with IV or oral corticosteroids
 - For **Grade 3-4** events, treat with intravenous corticosteroids for 24 to 48 hours.
 - When symptoms improve to Grade 1 or less, a steroid taper should be started and continued over no less than 4 weeks.

- **Renal Failure or Nephritis:**

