 - For **Grade 2** events, treat with corticosteroids.
 - For **Grade 3-4** events, treat with systemic corticosteroids.

- When symptoms improve to Grade 1 or less, steroid taper should be started and continued over no less than 4 weeks.

Management of Infusion Reactions: Signs and symptoms usually develop during or shortly after drug infusion and generally resolve completely within 24 hours of completion of infusion.

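### Section 5.3.1 scores a treatment-ending grade 3+ toxicity as no DLT once it resolves within 12 weeks, and the 6-week accrual pause has no separate criterion for being lifted

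*Combined protocol and SAP*

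**What the plan says.** **DLT definition.** Section 5.3.1 counts hematologic or non-hematologic "toxicity of grade 3 or above possibly attributable to drug that does not resolve within 12 weeks with or without steroids". Steroids must also be reducible to below 10 mg a day in the same period. The decision-rule paragraph repeats the 12-week condition. No clause makes permanent discontinuation a DLT in itself. A death would count, because it cannot resolve.

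**Decision rule.** Cohorts A and B are pooled. Section 5.3: "If < 2 DLTs are seen in the first 6 participants, enrollment to the rest of the cohorts will proceed". Section 5.3.1: "If no more than 1 of 6 participants experiences a DLT, full enrollment of the cohort may proceed". Two or more DLTs, at 3 or at 6 participants, stop enrollment for discussion between Merck and the overall PI.

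**6-week clause.** If a participant with a grade 3-5 toxicity cannot resume treatment within 6 weeks, "enrollment into cohorts A and B will be halted to allow for a full 12 week evaluation prior to further enrollment".

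**Permanent discontinuation.** Table 3 (Section 5.3.2) ends pembrolizumab without regard to recovery for:
- grade 3-4 pneumonitis, nephritis, infusion reaction and hepatic toxicity (footnote 1 sets a separate rule for some patients with liver metastases);
- grade 4 colitis, hypophysitis, hyperthyroidism and other drug-related toxicity.

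Table 4 (Section 5.5.6) says of a grade 3-4 infusion reaction: "Subject is permanently discontinued from further trial treatment administration".

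Other rows are not absolute. For hypothyroidism of grades 2-4, "Therapy with pembrolizumab can be continued while treatment for the thyroid disorder is instituted".

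**The concern.** The 12-week and steroid test in the DLT definition closely follows the discontinuation column of many Table 3 rows. It captures the slow route to stopping drug, where an event is held and fails to recover. It omits the immediate route, which Table 3 reserves for the events it treats as most serious. A grade 3 toxicity in the residual Table 3 row that is still present at 12 weeks is a DLT; grade 4 colitis that ends treatment and then recovers is not.

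The DLT count is the numeric rule for opening the rest of cohorts A and B: 2 × 15 = 30 planned places, less 6, leaves 24. If two of six participants lose pembrolizumab to toxicity and both recover, the count is 0. The halt for discussion with Merck and the overall PI is then not triggered by the count, and the run-in would be reported as showing no DLTs.

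**Working it through.** **Can these events resolve in time?** The protocol's own text suggests that some will. Section 5.8.3 says infusion reactions, with no grade given, "generally resolve completely within 24 hours of completion of infusion". For grade 3-4 hepatic events it gives 24 to 48 hours of intravenous steroid, then: "When symptoms improve to Grade 1 or less, a steroid taper should be started and continued over no less than 4 weeks". Since 12 − 4 = 8, a hepatic event that improves by about week 8 can be resolved and tapered by week 12 and so score 0.

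**Does the 6-week clause close the gap?** On its natural reading, a participant permanently off pembrolizumab cannot resume, so one such event pauses A/B accrual. The pause exists to allow a 12-week evaluation. The clause does not say what result of that evaluation allows restarting. The only stated clearing criterion is the DLT count, on which a resolved event is 0.

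**Size.** The plan gives no target DLT rate or operating characteristic, so there is no figure to reproduce.

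Inputs:
- n = 6, with the halt at 2 or more DLTs (Section 5.3.1). Stopping at 2 of 3 or at 2 of 6 is the same as X ≥ 2 of 6.
- p = chance per participant of a non-hematologic event in cycles 1-2 that must end pembrolizumab regardless of recovery. Not in the documents; assumed 2%, 5%, 10%.
- u = share of those events unresolved, or not tapered, at 12 weeks. Not in the documents; assumed 50% and 20%, with 0% as the bound.

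Section 10.1.1.1 lists pneumonitis, colitis and infusion reaction at 1-5% each, and liver and kidney inflammation below 1%, for pembrolizumab with no grade or time limit. It therefore fixes no grade 3-4 rate over six weeks. The 2% and 5% columns lie nearer to it; 10% is illustration.

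Formulas:
- Clear if every such event counted: P(X ≤ 1 | 6, p) = (1−p)^6 + 6p(1−p)^5.
- Clear as written: P(X ≤ 1 | 6, pu).
- Gap: the difference, which is the chance of 2 or more events but at most 1 DLT.
- Pause: 1 − (1−p)^6.

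Example, p = 0.05 and u = 0.5. All counted: 0.95^6 + 6(0.05)(0.95^5) = 0.7351 + 0.2321 = 0.9672. As written, at pu = 0.025: 0.9912. Gap: 0.9912 − 0.9672 = 0.0240.

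| | p = 2% | p = 5% | p = 10% |
|---|---|---|---|
| Clear, all events counted | 0.9943 | 0.9672 | 0.8857 |
| Clear as written, u = 50% | 0.9985 | 0.9912 | 0.9672 |
| Clear as written, u = 20% | 0.9998 | 0.9985 | 0.9943 |
| Gap, u = 50% | 0.0042 | 0.0240 | 0.0815 |
| Gap, u = 20% | 0.0054 | 0.0313 | 0.1086 |
| Gap, u = 0 (upper bound) | 0.0057 | 0.0328 | 0.1143 |
| Clear given 2+ events, u = 50% | 0.743 | 0.732 | 0.713 |
| Clear given 2+ events, u = 20% | 0.958 | 0.955 | 0.950 |
| Pause, at least one event | 0.114 | 0.265 | 0.469 |

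The conditional rows are high, but they condition on 2 or more events, which has probability 0.6%, 3.3% and 11.4% at the three rates.

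**The case against.** **Accrual is halted anyway.** A reader might infer that nothing stops enrollment after resolved treatment-ending events. The documents do not support that. The 6-week clause acts on a single participant, which is stricter than 2 of 6, and it is not worded as limited to the first six. This stands. What remains missing is a rule for lifting the halt and a required discussion at two such events.

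**The events would be seen.** SAEs go to the overall PI within 24 hours and to Merck within 2 working days (Section 10.3). The Data and Safety Monitoring Committee reviews quarterly, at cohort activation and on request, with calls after 3 patients (Section 10.5.1). The PI evaluates adverse events monthly (Section 12.1), and Section 4.6.1 allows termination for a health hazard. Section 5.3.1 says enrollment may proceed, which is permissive. These provisions make a silent restart unlikely. They give visibility and discretion, but none puts a resolved event into the count or says when the pause ends.

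**It is a design choice at one fixed dose.** No dose reductions are pre-specified, and a transient infusion reaction need not be called dose-limiting. That is arguable, but the plan does not explain why events its own tables treat as ending therapy are left out of the safety count.

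**The size is small and assumed.** This stands. A larger contrast is tempting: at a 30% event rate with 80% resolved, the halt probability is 4.6% as written against 58.0% if all such events counted. Nothing in the documents supports a 30% rate, and the 4.6% leaves out the 6-week pause.

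**Conclusion.** The concern holds in a limited form. As written, the run-in can clear after two or more treatment-ending non-hematologic toxicities that resolve, without the Merck and overall PI discussion that two DLTs would require, and a reported 0-1 of 6 would understate toxicity. The probability of this is about 0.4 to 3.3 points at assumed rates of 2-5%, with an upper bound of 11.4 points at 10%. These figures rest on assumed event rates, assumed resolution and independent participants. The reading of the text does not depend on them.

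The point does not extend to hematologic toxicity, to events whose Table 3 row allows continuing or restarting, or to the primary PD-L1 analysis. It should be fixed because the amendment is short and the run-in exists to establish the safety of the combination.

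**What to change.** **Add to Section 5.3.1:** a non-hematologic toxicity of grade 3 or above, possibly attributable to pembrolizumab or the combination, with onset in cycles 1-2, is a DLT whether or not it resolves if a Table 3 row, or Table 4, requires permanent discontinuation of pembrolizumab regardless of recovery. Limit infusion reactions to those caused by the pembrolizumab infusion. Section 5.5.6 applies the same guidance to cisplatin, carboplatin and etoposide, so without this limit a chemotherapy reaction could count.

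**Keep the 12-week clause** for hematologic toxicity, footnote 1 hepatic cases, and events whose row allows continuing or restarting, such as grade 4 hypothyroidism or grade 3-4 hyperglycemia. The row should decide. An event stopped only under the general Table 3 note on life-threatening events would still follow the 12-week test, but would appear in the review below.

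**State how the 6-week halt ends:** only after permanent discontinuations have been reviewed beside the DLT count with Merck and the overall PI.

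**Cost:** amendment wording, with no added patients or procedures. On the assumptions above, discussion halts rise by at most 0.6, 3.3 and 11.4 points at event rates of 2%, 5% and 10%. Some halts may be for renal or grade 4 events due to platinum-etoposide. The pembrolizumab list in Section 10.1.1.1 does not inform their frequency, so that part of the cost cannot be sized from the documents.
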